**Table 4-1 Treatment regimens**

Treatment regimen	Age (years)	Dose	Dose frequency
Prophylaxis	12-70 years	40 IU/kg	Once-weekly
Treatment of bleeds	12-70 years	Mild and moderate bleeds: 40 IU/kg Severe bleeds: 80 IU/kg Additional doses of 40 IU/kg can be given if there is no observed effect of the first dose.	When necessary
Surgery	12-70 years	At investigator's discretion (the following dosing guidelines can be used). Minor surgery: 40 IU/kg prior to the surgery. Additional doses can be given if needed. Major surgery: 80 IU/kg prior to the surgery. Two repeated doses of 40 IU/kg (in 1- to 3-day intervals) within the first week after surgery. Thereafter, the frequency of dosing may be extended to once weekly until bleeding stops and healing is achieved.	Pre-dose and when necessary

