#### **4.1.5 Treatment for surgery**

Major and minor surgery can be performed while participating in the trial. Use of FIX products other than nonacog beta pegol for surgery is not allowed. Patients undergoing surgical procedures will receive trial product as bleeding preventive treatment according to standard practice at the clinical site and/or at the investigator's discretion.

For dosing guidance in patients who need to undergo surgical procedures during the trial, investigators could refer to [Table 4-1](#) and WFH guidelines. As these guidelines are recommendations, non-compliance with them will not require any protocol deviations. Achieving higher FIX activity levels may be necessary depending on type of surgery and standard practice at the clinical site. The rationale is to replace the FIX activity in these patients up to FIX activity levels that are effective in preventing bleeding during and after surgery.

The specific treatment for each patient is decided by the investigator in collaboration with the surgeon. Surgery can be done at the clinical site, in another clinical department of the site or at another hospital. If a surgery takes place at another location than at the clinical site, the surgeon must be informed that the patient is participating in the trial, and the investigator should give instructions to the surgeon about the dosing treatment, the handling of the trial product and the efficacy and safety evaluation. It must be ensured that there is enough available trial product for the surgery, including the post-operative period. Please note the medication that is not permitted during the trial and surgery, see Section [7.1](#).

The maximum dose to be administered to a patient within 24 hours is 200 IU/kg, with a maximum individual dose of 80 IU/kg to be administered no more frequently than every hour.

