## 8.1.3 Surgery

Surgery should be performed at a dedicated surgery visit. See Section [1.2](#) (flowchart and [Table 1-2](#)) for procedures and assessments to be performed during and following a surgery visit. The following information will be recorded for each surgery:

- Type of surgery
- Indication for surgery
- Location of surgery
- Date of surgery and start and stop time

Surgical procedures should be performed by a surgeon in collaboration with the investigator.

Surgery should preferably be scheduled early in the week and early in the day for optimal conditions, e.g. support from the blood bank. Access to sufficient quantities of nonacog beta pegol should be ensured before undertaking surgery.

Blood samples for analysis of FIX activity will be collected on the day of surgery: pre-dosing (trough) and  $30\pm 5$  min (recovery) post-administration of the dose for surgery. These sampling time points are relative to completion of nonacog beta pegol administration, and actual time must be documented. Furthermore, blood samples for analysis of FIX activity (pre- and post-dose) will be collected for every post-surgery dose and upon return to assigned treatment at the end of the surgery period.

Blood samples for analysis of FIX inhibitors will be collected on the day of surgery and again upon return to assigned treatment at the end of the surgery period.

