5.4.1.4 FIX trough levels during PPX treatment

This endpoint will be evaluated based on data from Arm B only.

The FIX trough and recovery levels will be analysed by a mixed model on the log-transformed plasma FIX activity with patient as a random effect. The mean trough and recovery levels will be presented back-transformed to the natural scale together with the 95% confidence interval.

The following rules will be implemented for the analysis of trough and recovery levels:

- Pre-dose and post-dose values will be excluded if post-dose activity is \leq pre-dose activity
- Pre-dose and post-dose values taken less than 5 days or more than 9 days after last dose will be excluded
- Pre-dose and post-dose values taken less than twice the PPX treatment interval (14 days) after last treatment of a bleeding episode will be excluded
- Pre-dose and post-dose values taken within 2 weeks after surgery will be excluded
- Pre-dose and post-dose values taken in relation to the first exposure will be excluded
- FIX activity measured in defrosted plasma samples will be excluded

Furthermore, trough and recovery (30 minutes post-dose) levels measured at scheduled visits will be summarised and listed. Incremental recovery will be calculated and presented in summary tables and plots.

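### The post-surgery exclusion for trough and recovery is timed from the operation, not from the last extra dose, so a value with carry-over can pass every rule and enter the trough model

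*SAP*

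**What the plan says.** SAP 5.4.1.4 and Protocol 9.4.3.2 give the same exclusion list for the mixed model of log FIX activity. Three of its rules matter here.

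- Bleeds: values "taken less than twice the PPX treatment interval (14 days) after last treatment of a bleeding episode will be excluded".
- Surgery: "Pre-dose and post-dose values taken within 2 weeks after surgery will be excluded".
- Dosing gap: "Pre-dose and post-dose values taken less than 5 days or more than 9 days after last dose will be excluded".

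On dosing, Protocol Table 4-1 gives guidance for major surgery of 80 IU/kg beforehand, then "Two repeated doses of 40 IU/kg (in 1- to 3-day intervals) within the first week after surgery". It continues: "Thereafter, the frequency of dosing may be extended to once weekly until bleeding stops and healing is achieved". Protocol 4.1.5 adds: "As these guidelines are recommendations, non-compliance with them will not require any protocol deviations".

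On sampling, Protocol 8.1.3 collects FIX activity before and after dosing "for every post-surgery dose and upon return to assigned treatment at the end of the surgery period". Table 1-2 times its surgery assessments from the start of surgery and suggests days 2, 5, 7 and 14.

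SAP 5.7 has the date of return to regular treatment recorded. It uses that date for exposure time, ABR and haemostatic response, and does not mention trough levels.

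**The concern.** Carry-over depends on when the last extra dose was given, not on when the operation took place. The plan follows that principle for bleeds but not for surgery, although the surgical guidance adds more drug, and it gives no reason for the difference.

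The other rules do not fill the gap. The 5-to-9-day rule removes samples taken soon after a dose, but not the build-up from closely spaced doses followed by a normal weekly interval. Preventive surgical doses are not bleed treatment, so they do not trigger the bleed rule.

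A retained value of this kind is not a once-weekly steady-state trough, and the error runs in the favourable direction. FIX trough is a named secondary endpoint in about 15 patients, and comparison with the global pivotal trial is the stated purpose of the trial.

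**Working it through.** The plan has no figure of its own to reproduce. The check applies its exclusion rules to dosing calendars.

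**Inputs from the documents.** Weekly dose 40 IU/kg; 80 IU/kg on day 0 (surgery); two 40 IU/kg doses at 1- to 3-day intervals in the first week (Table 4-1); the exclusion rules above; 15 patients in Arm B (SAP 3).

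**Assumptions.** One compartment with linear first-order decay. Half-life 70, 85, 100 or 115 h. Whole-day timing. The original weekly day is kept, and a weekly dose falling on or before the last extra dose is skipped. Day 14 counts as within 2 weeks.

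**Step 1: which calendars leave a gap.** Let the extra doses fall on days L1 (1 to 3) and L2 (1 to 3 days later), with the weekly day at p = 1 to 7. That gives 9 × 7 = 63 calendars. The first weekly pre-dose sample after day 14 is on day 14 + p. The previous dose was on day 7 + p, so the gap is 7 days and the 5-to-9-day rule keeps the sample. It lies 14 + p − L2 days after the last extra dose, which is under 14 whenever p < L2. Counting the values of p below L2:

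- L1 = 1: 1 + 2 + 3 = 6
- L1 = 2: 2 + 3 + 4 = 9
- L1 = 3: 3 + 4 + 5 = 12

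The total is 27 of 63. This counts calendars; it is not a probability.

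**Step 2: size in one calendar.** Take surgery on day 0, extra doses on days 3 and 6, and weekly doses on days 8 and 15 (the last weekly dose before surgery was on day −6). The day-15 sample is 15 days after surgery, 7 days after the last dose and 9 days after the last extra dose. It passes every rule.

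With k = ln 2 / half-life and r = exp(−7k), k per day, and levels in dose units:

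- Steady-state trough: T = 40r / (1 − r)
- Day-15 level: L = 40r³/(1 − r) + 80e^(−15k) + 40e^(−12k) + 40e^(−9k) + 40e^(−7k)
- At 100 h: T = 18.15 and L = 1.77 + 6.60 + 5.43 + 8.95 + 12.48 = 35.23, so L/T = 1.94
- Recovery-level ratio: (L + 40) / (T + 40). Because T = (T + 40)r, this is also the trough ratio one week later, on day 22.

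| Half-life (h) | r | T | L | Day-15 trough ratio | Day-15 recovery ratio, and day-22 trough ratio |
|---|---|---|---|---|---|
| 70 | 0.190 | 9.35 | 17.20 | 1.84 | 1.16 |
| 85 | 0.254 | 13.63 | 25.98 | 1.91 | 1.23 |
| 100 | 0.312 | 18.15 | 35.23 | 1.94 | 1.29 |
| 115 | 0.363 | 22.82 | 44.61 | 1.95 | 1.35 |

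**Step 3: range.** Across the 27 calendars and four half-lives, the trough ratio runs from 1.23 (extra doses on days 3 and 6, p = 5, sampled on day 19, 70 h) to 1.95. For longer discretionary dosing, purely as illustration, 40 IU/kg every 3 days to day 12 and then weekly leaves a retained day-19 trough at 1.60 to 1.78 times.

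**Step 4: effect on the endpoint.** Assume 15 × 7 = 105 equally weighted values. One value inflated 1.8-fold multiplies the Arm B geometric mean by 1.8^(1/105) = 1.0056, or +0.6%. Three such values give 1.8^(3/105) = 1.017, or +1.7%. Within one patient with 7 values, 1.8^(1/7) = 1.09.

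**Step 5: what a 14-day clock from the last extra dose achieves.** It drops all 27 values. In those calendars the next weekly trough is at 1.04 to 1.35 times. In the other 36 calendars both clocks keep the same first value, at 1.14 to 1.67 times.

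**The case against.** The strongest reply is that the gap is narrow and its use in the model is not certain.

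- **Day 14.** A reader might infer that the day-14 sample suggested in Table 1-2 enters the model at about twice the true trough. On an ordinary reading, within 2 weeks covers day 14, and no suggested time in that table is later. The calculation above therefore relies on day 15 and beyond.
- **Many calendars are unaffected.** In 36 of 63 the two clocks agree on the first retained value. If weekly dosing restarts from the last first-week dose, they always agree. Minor surgery with a single dose in place of a weekly one gives a ratio of about 1.0. It would be wrong to say that inflated values will enter; they can.
- **The gap rule does work.** It removes the worst values. A day-15 sample during 3-day dosing would be more than three times steady state at 100 or 115 h, and it is dropped.
- **Are these samples in the model?** The endpoint concerns prophylaxis, Table 4-1 lists surgery as a separate regimen, and scheduled visits are 4 to 8 weeks apart. This stands in part: a sample must exist on the day. However, Protocol 8.1.3 takes one at every post-surgery dose and on return to assigned treatment. The model text is not limited to scheduled visits; only the separate summaries are.
- **What surgery means.** The rule does not define its starting point. Read as the end of the surgery period, most of the gap closes. But SAP 5.7 refers explicitly to the surgery period when it means that, and Table 1-2 counts from the start of surgery.

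**Conclusion.** The mismatch between the two clocks is in the text, and no other rule closes it. Under the documents' own major-surgery guidance, or under longer discretionary dosing, a pre-dose value just after day 14 can be retained at about 1.2 to 2.0 times the steady-state weekly trough, with smaller inflation of recovery. The direction is upward for every half-life tried.

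The consequence is small. It is limited to Arm B patients who have major surgery or several perioperative doses, and each such value shifts the Arm B geometric mean by under 1%. The plan tests no hypothesis, so no formal conclusion could change. A reader might infer that the trough endpoint is materially biased; the arithmetic does not support that unless many operations occur. The ratios rest on an assumed half-life and one-compartment decay. The count of 27 does not depend on half-life, but it does rest on the calendar assumptions. Nothing here bears on whether the surgical dosing is right.

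**What to change.** Replace the surgery line in SAP 5.4.1.4 and Protocol 9.4.3.2 with a rule to this effect: *Trough and recovery samples are left out if drawn up to and including day 14 after surgery, or fewer than 14 days after the last additional dose given in relation to surgery; the later limit applies. An additional dose is one beyond the once-weekly schedule.*

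The definition of an additional dose matters. Table 4-1 allows post-operative dosing to become once weekly, and those doses should not restart the clock and discard ordinary weekly troughs. State also that the day of surgery is day 0, as the hours in Table 1-2 imply, because SAP 5.7 calls it Day 1.

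The cost is one sentence in each document and a few more excluded values in operated patients. Protocol 6.4 already has all doses recorded in the eCRF, so no new data are needed. Dosing and sampling do not change. Some carry-over remains (Step 5), because 14 days is simply the standard the plan already accepts for bleeds.

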5.4.2 Secondary safety endpoints

Endpoint title	Time frame	Unit
Number of patients with inhibitory antibodies against FIX defined as titre ≥ 0.6 Bethesda units (BU)	From start of treatment (week 0) until end of treatment (up to week 50)	Count

Endpoint title	Time frame	Unit
Number of adverse events (AEs)	From start of treatment (week 0) until end of treatment (up to week 50)	Count
Number of serious adverse events (SAEs)	From start of treatment (week 0) until end of treatment (up to week 50)	Count

The safety endpoints will be evaluated based on data from both Arm A and Arm B.

5.4.2.1 Number of patients with inhibitory antibodies against FIX defined as Titre ≥ 0.6 BU

The rate of neutralising antibodies will be reported and a 1-sided 97.5% upper confidence limit will be provided based on an exact calculation for a binomial distribution. For the calculation of the inhibitor rate the nominator will include all patients with neutralising antibodies while the denominator will include all patients with a minimum of 10 exposures plus any patients with less than 10 exposures but with neutralising inhibitors.

5.4.2.2 AEs and SAEs reported during the trial

Treatment emergent AEs (TEAEs defined as AEs occurring after dosing with trial product) and treatment emergent SAEs (TESAEs) will be summarised by frequency of events and frequency of patients with any event. Similar summaries cross-classified by severity and by causal relation to trial product will be made.

Furthermore, listings will be provided displaying all TEAEs and TESAEs including pertinent clinical information.

5.4.3 Secondary pharmacokinetic endpoints

Pharmacokinetic parameters to be derived in the trial (Arm B only) are listed in [Table 2](#).

Table 2 Definition and calculation of pharmacokinetic parameters

Title	Time frame	Unit	Details
Incremental recovery (IR)	Single-dose: 30±10 minutes post injection at week 0 Steady-state: 30±10 minutes post injection at week 12	(IU/mL)/(IU/kg)	The increase in plasma FIX activity from pre-dose to 30 min post-dose divided by the dose injected. IR is calculated by subtracting the FIX activity (IU/mL) measured in plasma at time 0 from that measured at time 30 min after dosing and dividing this difference by the dose injected at time 0 expressed as IU/kg body weight.
FIX activity 30 min post-injection ($C_{30\text{min}}$)	Single-dose: 30±10 minutes post injection at week 0 Steady-state: 30±10 minutes post injection at week 12	IU/mL	The FIX activity recorded 30 min after end of injection. Expected to be the maximum FIX activity observed.
FIX activity 168 h post-injection ($C_{168\text{h}}$)	Single-dose: 168±24 hours post-injection at week 0 Steady-state: 168±24 hours post-injection at week 12	IU/mL	The FIX activity recorded 168 hours after end of injection. Expected to be the minimum FIX activity observed.
$AUC_{(0-\infty)}$	Single-dose: 0-168 hours post-injection at week 0 Steady-state: 0-168 hours post-injection at week 12	h·IU/mL	Area under the plasma activity versus time profile from time zero to infinity. Measure of total plasma exposure. $AUC_{(0-\infty)} = AUC_{(0-t)} + C_{(t)} / \lambda_z$, where $C_{(t)}$ is the last measurable activity.
$AUC_{(0-t)}$	Single-dose: 0-168 hours post-injection at week 0 Steady-state: 0-168 hours post-injection at week 12	h·IU/mL	Area under the plasma activity versus time profile from time zero to the last measurable activity. Measure of plasma exposure in the time interval 0 to last measurable activity. $AUC_{(0-t)}$ is calculated using the linear trapezoidal method from time 0 to the time for the last measurable activity. The activity at time 0 will be estimated by log-linear back extrapolation of the two initial post-administration activities. If the second value is not lower than the first value, the concentration at time 0 will be defined as the highest of these two.

Title	Time frame	Unit	Details
AUC _(0-168h)	Single-dose: 0-168 hours post-injection at week 0 Steady-state: 0-168 hours post-injection at week 12	h·IU/mL	AUC _(0-168h) is calculated using the linear trapezoidal method from time 0 to 168 hours. If FIX activities are not available up to 168 hours post-dose, the area under the missing terminal part of the curve will be determined by interpolation or extrapolation using a similar principle as for AUC _(0-inf) , where the terminal elimination rate constant, λ_z , is used given that there are sufficient measurements for the determination of the terminal elimination rate constant.
Accumulation ratio	0-168 hours post-injection at weeks 0 and 12		Accumulation ratio is calculated as AUC _(0-168h) at steady state/AUC _(0-168h) after a single dose.
Terminal half-life ($t_{1/2}$)	Single-dose: 0-168 hours post-injection at week 0 Steady-state: 0-168 hours post-injection at week 12	h	$t_{1/2} = \ln(2) / \lambda_z$, where λ_z is the terminal elimination rate constant. The terminal elimination rate constant will be estimated using linear regression on the terminal part of the log(activity) versus time profile.
Clearance (CL)	Single-dose: 0-168 hours post-injection at week 0 Steady-state: 0-168 hours post-injection at week 12	mL/h/kg	CL = Dose / AUC. Using AUC _(0-inf) for single-dose and AUC _(0-168h) for steady-state.
V_z	Single-dose: 0-168 hours post-injection at week 0 Steady-state: 0-168 hours post-injection at week 12	mL/kg	Apparent volume of distribution based on the terminal phase. $V_z = CL / \lambda_z$
V_{ss}	0-168 hours post-injection at week 12	mL/kg	Apparent volume of distribution at steady state. $V_{ss} = CL \cdot MRT$
%extrap	Single-dose: 0-168 hours post-injection at week 0 Steady-state: 0-168 hours post-injection at week 12	%	Percentage of AUC _(0-inf) determined by extrapolation. $AUC_{(t-inf)} / AUC_{(0-inf)}$

Title	Time frame	Unit	Details
MRT	Single-dose: 0-168 hours post-injection at week 0 Steady-state: 0-168 hours post-injection at week 12	h	Mean residence time. MRT = $AUMC/AUC_{(0-\infty)}$, where AUMC is the area under the first moment curve, i.e. the area under the curve $t \cdot C(t)$, calculated with the same method as $AUC_{(0-\infty)}$ (linear trapezoidal method + extrapolated area).
λ_z	Single-dose: 0-168 hours post-injection at week 0 Steady-state: 0-168 hours post-injection at week 12	1/h	Terminal elimination rate constant. The terminal elimination rate constant will be estimated using linear regression on the terminal part of the log(activity) versus time profile.

Single-dose pharmacokinetics will be based on the pharmacokinetic session at Visit 2, and steady-state pharmacokinetics will be based on the pharmacokinetic session at Visit 5.

The pharmacokinetic parameters will be calculated using plasma FIX activity obtained from one-stage clotting assay. The pharmacokinetic parameters will be derived according to a non-compartmental method, as described in [Table 2](#). The actual time points will be used in the calculations.

If any profiles and/or individual plasma FIX activities are excluded from the primary pharmacokinetic analysis, a sensitivity pharmacokinetic analysis will also be performed and reported based on all observed data. The primary pharmacokinetic analysis is based on the FAS excluding outliers.

Which specific pharmacokinetic data points and profiles that will be excluded will be defined prior to database lock. Profiles with pre-dose FIX activity >5% at Visit 2 (possibly indicating inadequate wash out) and profiles that are not indicative of a normal i.v. injection (i.e. clearly increasing plasma FIX activity initially) should be excluded. If a patient is treated with an additional dose during the pharmacokinetic session, the plasma concentrations after the occurrence will then be excluded. Furthermore, if the pharmacokinetic profile shows indications of an additional dose (e.g. clearly increased plasma FIX activity), the plasma concentrations after the occurrence will then also be excluded.

Individual and mean pharmacokinetic profiles will be presented graphically.

Furthermore, the mean pharmacokinetic endpoints will be summarised and individual pharmacokinetic endpoints will be listed.

5.5 Exploratory endpoints analysis

Not applicable.

5.6 Other safety analyses

All additional safety parameters such as laboratory parameters, vital signs and physical examinations will be summarised and listed.

5.7 Other analyses

Surgery

In relation to surgery the following will be recorded:

- Haemostatic effect evaluated on the four-point scale (excellent, good, moderate and none) and assessed by the investigator/surgeon on the day of surgery (Day 1) and on the last day in the post-operative period the patient is at the trial/surgery site.
- Loss of blood and requirements for transfusion on the day of surgery (Day 1) and during the post-operative period Days 2-7 or until the last day the patient is at the trial/surgery site, whatever comes first.

All records will be summarised and listed. The date of return to regular trial treatment needs to be recorded, to allow for the exclusion of major surgery period from exposure time and the calculation of ABR and haemostatic response.

5.8 Interim analyses

No interim analysis is planned.

5.8.1 Data monitoring committee

Refer to protocol Section 9.6

6 Supporting documentation

6.1 Appendix 1 List of abbreviations

ABR	Annualised bleeding rate
AE	Adverse event
AUC	Area under the curve
AUMC	Area under the first moment curve
BU	Bethesda unit
CDE	Centre of Drug Evaluation
CI	Confidence interval
CL	Clearance
CTR	Clinical trial report
CV%	Coefficient of variation in percent
FAS	Full analysis set
FIX	Coagulation factor nine
IR	Incremental recovery
LLOQ	Lower limit of quantification
LOCF	Last observation carried forward
MRT	Mean residence time
PPX	Prophylaxis
SAE	Serious adverse event
SAP	Statistical analysis plan
SAS	Safety analysis set
$t^{1/2}$	Terminal half life

TE Treatment emergent

TFL Tables, figures and listings

